7.4 Electronic self-rated version of the Columbia-Suicide Severity Rating Scale

The electronic self-rated version of the C-SSRS is used to reliably and consistently monitor subjects for suicidal ideation and behavior during the study.

The eC-SSRS assesses lifetime suicidality during an initial baseline evaluation (Visit 2 [Baseline]), and then prospectively monitors ideations and behaviors at subsequent follow-up assessments (Visit 9 [Week 48], Visit 13 [Week 96], Visit 17 [Week 144] and Visit 18 [EOT]). At each visit, the treating neurologist will review the responses provided by the subject and assess the findings. The eC-SSRS is a fully structured clinical interview designed and developed for electronic administration. Subjects will be asked to respond to standardized clinical questions aimed at measuring the severity of suicidal ideation (rated on a 5-point ordinal scale), the levels of suicidal behavior, and the category self-injurious behavior without suicidal intent. Any subject who reaches an eC-SSRS suicidal ideation score of 4 or above, or who responds “yes” on the eC-SSRS suicidal behavior item must be referred to an appropriate health professional who should make a decision on the management of the suicidal symptoms and recommend whether or not the subject should continue the treatment with the study drug.

It is recommended that the eC-SSRS is completed prior to any clinical assessments, after the WPAI:MS and SF-36v2TM have been completed. Preferably, subjects would complete the eC-SSRS while waiting for their appointment before any interaction with healthcare providers. It is recommended that the subject stays at site until the report has been reviewed by the PI / treating neurologist.

A sample of the eC-SSRS (in English) is provided as [Appendix 14](#). The data will be collected via electronic data capture and processed centrally by a vendor who will send the results to Actelion.

Actelion has been granted a license agreement for the use of the eC-SSRS.

7.5 Quality of life assessments

7.5.1 36-Item Short Form Health Survey v2 (SF-36v2™)

The SF-36v2™ Questionnaire (SF-36v2™ Health Survey© 1996, 2000 by Medical Outcomes Trust and Quality Metric Incorporated) is used to assess the subject's quality of life. The SF-36v2™ will be completed by the subject at Visit 2 (Baseline), at Visit 6 (Week 12), Visit 7 (Week 24), Visit 9 (Week 48), and every 24 weeks thereafter up to Visit 17 (Week 144), and at Visit 18 (EOT) and at unscheduled visits due to relapses (R1, R2, etc.).

In the SF-36v2™ Questionnaire, subjects are instructed to rate their health and capacity to perform activities of daily living in eight domains including physical functioning, physical role limitations, bodily pain, general health, vitality, social functioning, emotional role limitations, and mental health during the last 4 weeks. Raw domain scores are determined and transformed to a 0–100 scale as described in the SF-36v2™ manual [Maruish 2011]. Individual domain scores are used to determine the physical and mental component summary scores as described in the SF-36v2™ manual [Maruish 2011].

It is preferable that the SF-36v2™ Questionnaire is completed prior to any clinical assessments, after the WPAI:MS have been completed. Preferably, subjects would complete the SF-36v2™ while waiting for their appointment before any interaction with health care providers to avoid any potential bias in their responses.

The SF-36v2™ with a 4-week recall period will be used. A sample of the SF-36v2™ (in English) is provided as [Appendix 10](#). The questionnaire will be administered in an electronic format. The data from the electronic device will be collected by the vendor who will send the results to Actelion.

Actelion has been granted a license agreement for the use of the SF-36v2™ Questionnaire. The individual questionnaires will be completed only in countries for which validated translations are available.

7.6 Pharmacoeconomic assessments

7.6.1 Work Productivity and Activity Impairment Questionnaire: Multiple Sclerosis V2.0

The WPAI:MS is a six-question patient-reported quantitative assessment of the amount of absenteeism, presenteeism, work productivity loss and activity impairment attributable to MS during the previous 7 days.

Actelion has adapted the specific health version of the WPAI version 2, which was developed by Reilly Associates for MS.

The WPAI:MS will be completed by the subject at Visit 2 (Baseline), at Visit 6 (Week 12), Visit 7 (Week 24), Visit 9 (Week 48), and every 24 weeks thereafter up to Visit 17 (Week 144), and at Visit 18 (EOT).

WPAI:MS outcomes are expressed as impairment percentages, with higher numbers indicating greater impairment and less productivity, i.e., worse outcomes.

It is preferable that the WPAI:MS Questionnaire is completed prior to any clinical assessments. Preferably, subjects would complete the WPAI:MS while waiting for their appointment before any interaction with health care providers to avoid any potential bias or impact of interventions in their responses.

A sample of the WPAI:MS (in English) is provided as [Appendix 11](#). The questionnaire will be administered in an electronic format. The data from the electronic device will be collected by the vendor who will send the results to Actelion.

Actelion Pharmaceuticals has notified the developer about the use of the instrument in this study. No license is required for the administration of the instrument. The individual questionnaires will be completed only in countries for which validated translations are available.

7.6.2 Health care resource utilization

Health care resource utilization data, including number of intensive care unit (ICU) admissions for MS relapses and emergency medical facility visits for MS will be collected at Visit 2 (Baseline), Visit 4 (Day 15) and at every visit thereafter up to Visit 18 (EOT) as well as at unscheduled visits due to relapse (R1, R2, etc.).

Subjects will be asked to report any hospital visit, length of stay, any visits to emergency medical services facilities due to MS since the last study visit, the dates will be captured in the eCRF. Hospitalization due to MS relapses will be captured in the eCRF including the length of stay and any admissions to ICU.

7.7 Pharmacokinetic and pharmacodynamic assessments

7.7.1 Pharmacokinetic assessments

PK samples will be collected during this study for all subjects, in order to provide information about study drug exposure in the target population. Blood samples will be collected pre-dose at Visit 6 (Week 12), Visit 7 (Week 24), Visit 9 (Week 48), Visit 13 (Week 96), Visit 17 (Week 144), Visit 18 (EOT) and at Visit 20 (FU). Additionally, at Visits 3 and 6 (Day 1 and Week 12), PK samples will be drawn 3 hours (\pm 15 minutes) post-dose.

When possible, a PK sample will be collected for all subjects experiencing SAEs. In this event, the sample should be collected pre-dose, as early as possible after SAE onset, and no later than 7 days after the last dose of study drug.

Details of the collection and shipment of the samples will be described in the laboratory manual. The tubes and labels for the sampling will be provided by the central laboratory.

The date and the time of blood sample collection will be entered in the eCRF, as well as the status of the patient (fed or fasted). The date and time of the last study treatment dosing before blood draw will be entered in the eCRF.

The concentration of ponesimod in plasma will be determined by a validated liquid chromatography-tandem mass spectrometry assay by PRA Health Sciences – Early Development Sciences, bioanalytical laboratory. The lower limit of quantification is 1 ng/mL.

Note:

The 3-hour PK sample collected on Day 1 or on the first day of re-initiation of study drug when post-dose monitoring is required should be taken by the first-dose administrator, the first-dose administrator nurse or another person not involved in the clinical care and management of the study subject.

7.7.2 Pharmacodynamic assessments

7.7.2.1 Total lymphocytes

The main PD marker is total lymphocyte count, which will be measured as part of the hematology tests [see Section 7.3.13.2].

7.7.2.2 Blood lymphocyte subsets

Blood samples for lymphocyte subset analysis will be taken from approximately 200 subjects at Visit 2 (Baseline), Visit 6 (Week 12), Visit 7 (Week 24), Visit 9 (Week 48), Visit 13 (Week 96), Visit 17 (Week 144), Visit 18 (EOT), Visit 19 (FU7d), and at Visit 20 (FU). Participation in the sub-study will be mandatory for all subjects until at least the first 200 subjects are randomized [see Section 3.6.1] to the main study. If applicable, lymphocyte subsets will also be assessed at the corresponding visits in the PTOP (Visits 6A, 7A, 9A, 13A, 17A, and 18A).

The site staff will ship the blood samples to the central laboratory for analysis. T cell, B cell, and NK cell counts will be analyzed as well as T cell subsets (e.g., CD4⁺ naïve, CD4⁺ effector memory, CD4⁺ central memory, CD8⁺ naïve, CD8⁺ effector memory, CD8⁺ central memory, CD8⁺ terminally differentiated effector memory, Th17 cells, Treg cells, and Th1 cells), will be analyzed by fluorescence activated flow cytometry using a combination of cell surface markers. Other lymphocyte subsets may also be analyzed.

Selected lymphocyte subsets may also be analyzed functionally *ex vivo* (e.g., production of cytokines). Results from the lymphocyte subsets sub-study will be blinded to site staff and the sponsor until study closure.

7.8 Total blood volume

The total blood volume to be drawn per subject during the entire course of the study is described in [Table 7](#).

Table 7 Total blood volume to be drawn per subject

Main study			
Test	Number of tests	Volume per test	Total volume per test throughout the study
Viral serology at Visit 1 (Screening)	1	7.5 mL	7.5 mL
Interferon gamma release assay for tuberculosis at Visit 1 (Screening)	1	3 × 1 mL	3 mL
Serum sample at Visit 2 (Baseline) ¹	1	5 mL	5 mL
Hematology ²	19	2 mL	38 mL
Blood chemistry ³	19	2.5 mL	47.5 mL
Lymphocytes ⁴	3	2 mL	6 mL
INR	19	1.8 mL	34.2 mL
Ponesimod PK	9	3 mL	27 mL
Vaccine specific Antibody titers ⁵	2	5 mL	10 mL
JCV serology	5	5 mL	25 mL
Total blood volume drawn throughout the main study: 203.2 mL^{6,7}			

Lymphocyte subsets sub-study (approximately 200 subjects)

Test	Number of tests	Volume per test	Total volume per test throughout the study
Lymphocyte subsets	9	6 mL	54 mL
Additional blood volume drawn for the sub- study: 54 mL			

1. To be stored at the central laboratory for potential retrospective analyses of viral serology titers in the event of infections.
2. Additional samples may be needed in the event of lymphocytes < 200 cells/ μ L.
3. Includes serum pregnancy test at Visit 1 (Screening), if needed.
4. Blood samples for lymphocyte counts are required to obtain 4-weekly (\pm 3 days) lymphocyte counts up to Week 24.
5. Additional samples may be taken in the event of a vaccination with a non-live vaccine.

6. If the blood sample cannot be evaluated (e.g., is lost or deteriorated) additional samples may need to be taken if deemed necessary by the investigator.
7. In the event of a positive Hepatitis C antibody test, site can draw an additional confirmatory blood sample (2.5 mL) for testing of Hep C viral RNA.

INR = International Normalized Ratio; PK = pharmacokinetics

No genomic testing will be performed on any blood sample collected during this study.

8 SCHEDE OF VISITS

A tabulated summary of all visits and assessments described in the following sections is provided in [Table 1](#), [Table 2](#) and [Table 3](#). The schedule of visit dates should be established at the time of Visit 1 (Screening). To the extent possible, subjects will be expected to adhere to the established visit schedule.

The timepoint for every visit is defined taking as a reference Day 1 (Visit 3), which is the day of randomization.

When scheduling the different assessments for a subject visit, the following should be taken into account:

- When applicable, the subject must come to the clinic before the morning administration of study drug.
- At Visit 3 (Day 1) and on the days of re-initiation of study drug when post-dose monitoring is required (if applicable), the assessments during the visits will be divided into two parts: before (pre-dose) and after (post-dose) the administration of the study drug, which will be taken at the site on the day of visits.
- At other visits, ECGs, SBP/DBP, PFTs, blood drawings for hematology and biochemistry, along with all other assessments, are to be performed pre-dose.
- When applicable, PK sampling is to be done pre-dose. At Visit 3 (Day 1) PK sampling is to be drawn 3 hours post-dose. At Visit 6 (Week 12) PK sampling must be drawn on the same day as pre-and post-dose ECGs and SBP/DBP are performed.
- Resting time:
 - When the subject is to go to another department within the hospital for a specific test, sufficient time should be allowed for the subject to rest prior to the examination.
 - Sufficient resting time should be allowed between the walking assessments for MSFC and EDSS and other assessments (PFTs, ECGs, and BP).
 - Sufficient time between blood drawing and cardiac assessments (i.e., ECGs and/or BP measurement) is to be allowed.
- Preferably, questionnaires will be completed by the subject in the morning prior to any other protocol-mandated assessment and prior to any discussion with the

investigator or treating neurologist. Subjects will provide responses to the questionnaires while waiting for their appointment. Questionnaires should preferably be completed in the following order:

- WPAI:MS
- SF-36v2™
- eC-SSRS

To ensure compliance, at each visit the study personnel must remind WOCBP to use the methods of contraception defined for this study. The reminders must be documented in the hospital chart.

It is permitted to re-screen subjects once if the reason for non-eligibility was transient (e.g., abnormal laboratory test, insufficient wash-out period of a forbidden medication), provided that documented authorization has been received from Actelion. Re-screening requires re-consenting i.e., a new ICF must be signed by the subject and by the investigator. All pre-randomization assessments do not need to be repeated at the time of re-screening if they were performed within 90 days or within 37 days for laboratory (i.e., hematology, blood chemistry, and pregnancy test). The guidance indicating which test needs to be repeated at the time of the re-screening authorization is provided in [Appendix 15](#).

The randomization must occur within 45 days from the date of Visit 1 (Screening; i.e., date of signature of the informed consent) or, in case of re-screening, within 45 days from the date of re-screening (i.e., date of signature of the new informed consent).

Unscheduled visits may be performed at any time during the study. Depending on the reason for the unscheduled visit (e.g., AE), appropriate assessments will be performed based on the judgment of the investigator and the results will be recorded in the CRF. After an unscheduled visit, the regular scheduled study visits must continue according to the planned visit and assessment schedule.

[figure not shown]
8.1 Pre-randomization period

The pre-randomization period must take place within 45 days prior to randomization and include the Visit 1 (Screening), Visit 2 (Baseline) and pre-dose assessments of Visit 3 (Day 1).

All pre-randomization assessments performed at Visit 1 (Screening) and Visit 2 (Baseline) may be conducted on days differing from the actual Visit 1 (Screening) and Visit 2 (Baseline) dates. All baseline assessments, including the ECG and blood pressure performed pre-dose on first day of dosing at Visit 3 (Day 1) must be performed before randomization [see [Figure 4](#)].

The start of screening occurs on the day the first screening assessment was performed (i.e., signature of informed consent).

Figure 4 Timing of the pre-randomization assessments

8.1.1 Visit 1 (Screening)

Visit 1 (Screening) will be performed at maximum 45 days prior to randomization. The Visit 1 (Screening) date is defined as the date of start of pre-randomization period (i.e., signature of the informed consent). During this visit, subject informed consent will be obtained, and the assessments required for the determination of subject eligibility will be performed. These assessments may generally be performed on separate days within the pre-randomization period.

Visit 1 (Screening) includes:

- After discussing the study with the investigator and after agreeing to study participation by signing the ICF, subjects will be assigned a subject number by the IRT provider. It is the responsibility of the investigator to obtain written informed consent prior to any screening assessment. The subject number will identify the subject throughout the study. In case of re-screening [see Section 8], the subject number assigned during the first screening procedure will be retained.
- Review of MS diagnosis and McDonald 2010 criteria.

- Recording of demographics, medical history, smoking status, and disease characteristics.
- Recording of previous and concomitant medications [see Section [5.2.2](#)].
- EDSS/FS (performed by the efficacy assessor).
- SBP/DBP.
- Body weight and height.
- Physical examination.
- Body temperature.
- Ophthalmological examination (under the responsibility of the ophthalmologist).
- Hematology (including lymphocytes), blood chemistry, and serum pregnancy test for WOCBP.
- TB test.
- Viral serology.
- Urinalysis.
- 12-lead ECG.
- MSFC and SDMT (first test practice).
- FSIQ-RMS; subjects who appear eligible based on the assessments made during this visit will be provided with the FSIQ-RMS. Once the results from the laboratory assessments confirm the subject's eligibility, and provided no other assessment performed in the meantime excludes the subject, the site coordinator will contact the subject to instruct him/her to start the completion of the FSIQ-RMS [see Section [7.2.6](#)].
- CXR (any CXR performed within 90 days prior to Visit 1 [Screening] can be used). In case of re-screening, CXR does not need to be repeated if it was performed within 90 days prior to the date of re-screening.
- Recording of AEs/SAEs: all AEs/SAEs occurring after signing of the ICF are to be reported in the eCRF and on an SAE form, if applicable.

The principal investigator / treating neurologist must check the inclusion/exclusion criteria. The next visit (Visit 2 [Baseline]) will only be scheduled if the subject meets all the eligibility criteria. If applicable, the date of screening failure will be collected in the IRT system and in the eCRF; additionally, the reasons for screening failure will be documented in the eCRF (screening information is collected for all screening failure subjects).

8.1.2 Visit 2 (Baseline)

Visit 2 (Baseline) will be performed anytime within the pre-randomization period. The date of EDSS assessment defines the date of the visit. During this visit, the inclusion and exclusion criteria will be confirmed, and baseline assessments will be performed and

recorded. While the assessments may generally be performed anytime during the pre-randomization period [see [Figure 4](#)], the following points should be considered:

- All Visit 1 (Screening) assessments repeated at Visit 2 (Baseline) with the exception of hematology and blood chemistry laboratory assessments (e.g., 12-lead ECGs, physical examination, SBP/DBP) must be performed at least 7 days after the Visit 1 (Screening) assessments.
- Hematology and blood chemistry laboratory assessments at Visit 2 (Baseline) must be performed at least 21 days after the hematology and blood chemistry laboratory assessments performed at Visit 1 [Screening; see [Section 4.3](#)].
- Similarly, for WOCBP, the urine pregnancy test at Visit 2 (Baseline) must be performed at least 21 days after the serum pregnancy test performed at Visit 1 (Screening).
- MSFC performed at Visit 2 (Baseline) must be performed at least 5 days after the assessment at Visit 1 (Screening) and at least 5 days before the assessment at Visit 3 (Randomization).

Visit 2 (Baseline) includes:

- WPAI:MS (subject completes the questionnaire prior to any clinical assessments or interaction with health care providers, preferably while waiting for their appointment).
- SF-36v2TM (subject completes the questionnaire after WPAI:MS, prior to any clinical assessments or interaction with health care providers, preferably while waiting for their appointment).
- eC-SSRS (subject completes the questionnaire after WPAI:MS and SF-36v2TM prior to any clinical assessments or interaction with health care providers, preferably while waiting for their appointment).
- Recording of change in previous and concomitant medications since Visit 1 [Screening; see [Section 5.2](#)].
- EDSS/FS (performed by the efficacy assessor).
- MS relapse.
- Health care resource utilization
- SBP/DBP.
- 12-lead ECG.
- Physical examination.
- Body temperature.
- Body weight.
- OCT (under the responsibility of the ophthalmologist).

- Dermatological examination (performed by the dermatologist). In case of re-screening, dermatological examination does not need to be repeated if dermatological examination from initial screening was performed within 90 days prior to the date of re-screening.
- Hematology (including lymphocytes), blood chemistry.
- Lymphocyte subsets (only at sites participating in sub-study).
- JCV serology.
- Urine pregnancy test for WOCBP.
- Additional serum sample for potential retrospective analysis of viral serology titers.
- Spirometry.
- MRI.
- MSFC and SDMT (second practice test).
- FSIQ-RMS.
- Recording of AEs/SAEs: all AEs/SAEs occurring after signing of the ICF are to be reported in the eCRF and on the SAE form, if applicable.

The principal investigator / treating neurologist must check all inclusion/exclusion criteria. The next visit (Visit 3) will only be scheduled if the subject meets all the eligibility criteria assessed at this time. Date of screen failure will be collected in the IRT system and in the eCRF; additionally, the reasons for screening failure are documented in the eCRF (screening information is collected for all screening failure subjects).

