subjects who appear eligible based on the assessments made during this visit will be provided with the FSIQ-RMS. Once the results from the laboratory tests confirm the subject's eligibility, and provided no other assessment performed in the meantime excludes the subject, the site coordinator will contact the subject to instruct him/her to start the completion of the FSIQ-RMS. At home, the subject will complete the symptom domain of the FSIQ-RMS for 7 days (i.e., section 1 of the questionnaire). On the 7th day, the subject will also complete the impacts domain of the FSIQ-RMS (i.e., section 2 of the questionnaire).

- (5) Healthcare resource utilization data, including number of hospital visits, length of stay, number of Intensive care unit admissions for MS relapses and emergency medical services facility visits for MS.
- (6) Any CXR that has been performed within 90 days prior to Visit 1 (Screening) can be used (in this case, no need to repeat CXR at Visit 1 [Screening]).
- (7) Dermatological examination to be performed by a dermatologist [see Section 7.3.12]. In case of re-screening, skin examination does not need to be repeated if skin examination from initial screening was performed within 90 days prior to the date of re-screening.
- (8) Height only at Visit 1 (Screening).
- (9) SBP/DBP: Pre-dose and hourly (\pm 15 minutes) for at least 4 hours post-dose and up to 12 hours.
- (10) Only pre-dose ECGs at all visits except Visit 3 (Day 1), and Visit 6 (Week 12).
- (11) Pre-dose and hourly (\pm 15 minutes) for at least 4 hours post-dose ECGs and up to 12 hours on Day 1. Pre-dose and 3 hour (\pm 15 minutes) post-dose at Week 12.
- (12) OCT and/or ophthalmological examination to be performed at any visit in the presence of visual symptoms suggestive of macular edema or active uveitis.
- (13) Total lymphocyte counts will be tested every 4 weeks (\pm 3 days) up to Week 24 (i.e., additional lymphocyte tests will be performed at Week 8, Week 16, and Week 20) and every 12 weeks thereafter.
- (14) Lymphocyte subset analysis will be performed on a subset of at least 200 subjects randomized to the main study.
- (15) Serum pregnancy test at Visit 1 (Screening), urine pregnancy test at all subsequent visits. Urine pregnancy tests (performed at home) on a 4-weekly basis (\pm 4 days) between the visits during the study (results of the pregnancy test to be communicated by telephone call to the principal investigator / treating neurologist).

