5. Ongoing known bacterial, viral or fungal infection (with the exception of onychomycosis and dermatomycosis), confirmed positive hepatitis B surface antigen test at Visit 1 (Screening; unless hepatitis B vaccination has occurred within 4 weeks prior to a positive screening test and a repeat hepatitis B surface antigen test performed \geq 2 weeks after the initial test has been negative) or hepatitis C antibody tests at Visit 1 (Screening).
6. Congenital or acquired severe immunodeficiency or known human immunodeficiency virus (HIV) infection or positive HIV testing at Visit 1 (Screening).
7. Negative antibody test for varicella-zoster virus at Visit 1 (Screening).
8. Known PML infection or evidence of new neurological symptoms or MRI signs within 6 months prior to randomization which are compatible with a diagnosis of PML infection.

Malignancy

9. History or presence of malignancy (except for surgically excised basal or squamous cell skin lesions), lymphoproliferative disease, or history of total lymphoid irradiation or bone marrow transplantation.
10. Presence of pre-cancerous (e.g., actinic keratosis, atypical moles) or cancerous skin lesions (e.g., basal cell carcinoma, squamous cell carcinoma) at Visit 2 (Baseline).

Ophthalmologic

11. Presence of macular edema.

Cardiovascular

12. Any of the following cardiovascular conditions:
 - Resting HR < 50 bpm as measured by the pre-randomization 12-lead ECG on Day 1;
 - Myocardial infarction within 6 months prior to randomization or current unstable ischemic heart disease;
 - Cardiac failure (NYHA class III or IV) or any severe cardiac disease at the time of Visit 1 (Screening) or randomization;
 - History or presence of valvular heart disease associated with significant symptoms or hemodynamic change according to investigator judgment;
 - History or presence of cardiac rhythm disorders (e.g., sino-atrial heart block, symptomatic bradycardia, atrial flutter or atrial fibrillation, ventricular arrhythmias, cardiac arrest);
 - Presence of second-degree AV-block or third-degree AV-block or a QTcF interval > 470 ms (females), > 450 ms (males) as measured by 12-lead ECG at Visit 1 (Screening), Visit 2 (Baseline) or by the pre-dose ECG at Visit 3 (Randomization / Day 1);

- History of syncope associated with cardiac disorders;
- Systemic arterial hypertension not controlled by medication according to investigator judgment.

Metabolic

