7.3.12 Dermatological examination

A complete skin examination will be performed by a dermatologist at Visit 2 (Baseline), Visit 9 (Week 48), and every 48 weeks thereafter until Visit 17 (Week 144), and at Visit 18 (EOT). If applicable, dermatological examination will also be performed at corresponding visits in the PTOP. In addition, unscheduled complete skin examination may be performed by the dermatologist at any time during the study (Visits U1, U2, etc.).

The purpose of the skin examination prior to randomization is to record the pre-existing lesions, exclude subjects with suspicious skin lesions (pre-cancerous, cancerous) from the study, and to document a baseline assessment. In case of re-screening, skin examination does not need to be repeated if skin examination from initial screening was performed within 90 days prior to the date of re-screening unless the screen failure was due to a skin lesion. If the screen failure was due to a pre-cancerous skin lesion or basocellular carcinoma that was then completely excised, the subject may be re-screened, in which case a new dermatological examination with focus on the excised skin lesion(s) has to be performed during pre-randomization.

In the event of findings of suspicious or pre-cancerous or cancerous skin disorders observed at any visit during the study, the dermatologist will conduct further examination, as per local standard practice, including the taking of skin biopsies if required to rule out or confirm a diagnosis.

All examinations will be documented in the source documents of the subject. Dermatological examination should be recorded in the eCRF as normal or abnormal. If an abnormality is found, it should be specified on the corresponding eCRF page. Clinically relevant findings meeting the definition of an AE (new AE, or worsening of previously existing condition; see Section 10.1) will be recorded accordingly on the AE page of the eCRF.

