Appendix 15 Guidance for re-screening

It is permitted to re-screen subjects once if the reason for non-eligibility was transient (e.g., abnormal laboratory test, insufficient wash-out period of a forbidden medication), provided that documented authorization has been received from Actelion. Re-screening requires re-consenting i.e., a new Informed Consent Form must be signed by the subject and the PI.

- If the screening failure was due to a laboratory result (i.e., one or more hematology variables and/or one or more biochemistry variables were out of eligibility range) from Visit 1 (Screening):
 - All hematology and/or blood chemistry assessments from Visit 1 (Screening) need to be repeated and will then be used for assessing eligibility.
 - Other pre-randomization assessments do not need to be repeated if performed within 90 days (with the exception of 12-lead ECG and pregnancy test which should be performed within 37 days) prior to the date of re-screening and if their outcome was not exclusionary.
- If the screening failure was due to a laboratory result from Visit 2 (Baseline):
 - Laboratory assessments from Visit 2 (Baseline) must be repeated.
 - Laboratory assessments from Visit 1 (Screening) must be repeated unless performed within 37 days prior to the re-screening. In this case, laboratory assessments at Visits 1 and 2 (re-screening) must be performed at least 21 days apart.
 - Other pre-randomization assessments do not need to be repeated if performed within 90 days (with the exception of 12-lead ECG and pregnancy test which should be performed within 37 days) prior to the date of re-screening and if their outcome was not exclusionary.
- If the reason for screening failure was due to an assessment other than laboratory tests:
 - The assessment leading to the screening failure has to be repeated.
 - Other pre-randomization assessments do not need to be repeated if performed within 90 days prior to the date of re-screening (with the exception of 12-lead ECG, hematology, blood chemistry and pregnancy test which should be performed within 37 days) and if the outcome was not exclusionary.

- If the screening failure was due to more than one assessment (e.g., laboratory and dermatological assessments) and the re-screening was authorized by Actelion:
 - All pre-randomization assessments have to be repeated.

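### Section 8.1.2 and Table 1 footnote 7 waive the repeat skin examination at re-screening without the skin-lesion exception in Section 7.3.12, and contrary to Appendix 15

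*Protocol*

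**What the plan says.** Four places in the protocol deal with repeating the skin examination when a subject is re-screened.

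- **Section 8.1.2 (Visit 2 list):** the "dermatological examination does not need to be repeated if dermatological examination from initial screening was performed within 90 days" of the re-screening date. It states no exception and does not refer to Section 7.3.12.
- **Table 1, footnote 7:** "skin examination does not need to be repeated if skin examination from initial screening was performed within 90 days". The preceding sentence of the footnote cites Section 7.3.12, but for who performs the examination.
- **Section 7.3.12:** the same waiver, limited to an examination "within 90 days prior to the date of re-screening unless the screen failure was due to a skin lesion". For a pre-cancerous lesion or basal cell carcinoma that has been completely excised, the subject may return, and "a new dermatological examination with focus on the excised skin lesion(s) has to be performed during pre-randomization".
- **Appendix 15:** for a failure on an assessment other than a laboratory test, "The assessment leading to the screening failure has to be repeated". Its 90-day relief covers only the other assessments, and only if their outcome was not exclusionary.

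Section 8 also bears on this. It opens with a general 90-day relief, sends the site to Appendix 15 for which tests to repeat, requires documented sponsor authorization, and sets a limit of 45 days from re-screening to randomization.

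**The concern.** The waiver without the exception stands in the two places a site is most likely to have open when it plans Visit 2: the visit list and the assessment table. In the one situation where the exception matters, the examination being reused is the one that found the exclusionary lesion.

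Two things are at stake. The first is eligibility: exclusion criterion 10 concerns pre-cancerous or cancerous skin lesions at Visit 2, and under the visit list the only dermatological evidence for it would predate the excision. The second is the safety data: Appendix 5 lists skin malignancy among the adverse events of special interest, and Section 10.1.1 counts a condition diagnosed during the study as an adverse event even if it was there beforehand. A residual lesion first diagnosed on treatment would therefore enter the safety tables.

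**Working it through.** There is no planned figure to reproduce. The check is to apply each instruction to the same subject.

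**Test case.** A subject is examined on day 0 and fails for a pre-cancerous lesion. The lesion is completely excised. The subject is re-screened on day 60, so the earlier examination is 60 days old, inside the 90-day window.

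| Place | Applied to this subject | Repeat examination? |
|---|---|---|
| Section 8.1.2 | 60 is within 90; no exception stated | Not needed |
| Table 1 footnote 7, waiver sentence | 60 is within 90; no exception stated | Not needed |
| Section 7.3.12 | Failure was due to a skin lesion, so the waiver does not apply | Required |
| Appendix 15 | The examination is the assessment that caused the failure | Required |

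The 90-day window is the same wherever this waiver is stated. Only the exception differs, so the conflict is confined to re-screened subjects whose screen failure was due to a skin lesion. For other re-screened subjects, Sections 8.1.2 and 7.3.12 agree.

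**Age of the reused examination.** It may be up to 90 days old at re-screening, and randomization may follow up to 45 days later: 90 + 45 = 135 days at most.

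**Next looks at the skin.** Section 7.3.12 schedules the dermatological examination at Visit 2, then Week 48 and every 48 weeks, and at end of treatment. Section 7.3.9 includes the skin in the physical examination, which is scheduled at Week 24 and every 24 weeks. The first scheduled inspection after randomization is therefore at Week 24, and the first scheduled dermatological examination at Week 48.

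**Likely origin.** The amendment rationale says the clarification was made in Section 7.3.12, so that the examination at re-screening would confirm successful excision. Section 7.3.12 is in the list of amended sections; Section 8.1.2 is not. This is cited only for the sponsor's stated purpose. The conflict lies in the current text.

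**The case against.** The best reply is that the protocol already guards against the error. Re-screening needs documented sponsor authorization, and Section 8 names Appendix 15 as the guide to what is repeated. Footnote 7 points to Section 7.3.12, where the exception stands. No eligibility criterion may be waived, and the investigator checks the criteria at Visit 2 and again at Visit 3. Moreover, the old examination found the lesion, so relying on it documents that criterion 10 excludes the subject. On this view two summaries lag behind a clear rule.

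Most of this stands, and it limits how often the error could occur. It does not remove the conflict. Section 8.1.2 has no pointer to Section 7.3.12, and Section 8 itself begins with a general 90-day relief. Criterion 10 asks about the skin at Visit 2, after the excision. Under the visit list the investigator would have to judge that without a dermatological examination made since the excision.

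A reader might go further in three ways that the documents do not support.

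- **That a subject would be randomized with nobody verifying the excision.** This ignores the safeguards above. What could be missing is the dermatological examination.
- **That a lesion would go unseen for 48 weeks.** Only the scheduled dermatological examination is that far off. A physical examination covering the skin falls at Week 24, and Section 7.3.12 allows unscheduled skin examinations at any time.
- **That Section 7.3.12 contradicts exclusion criterion 9 on squamous cell lesions.** Criterion 9 concerns history or presence of malignancy, "except for surgically excised basal or squamous cell skin lesions". Section 7.3.12 names pre-cancerous lesions and basal cell carcinoma as cases in which a subject may return, but does not say that these are the only ones.

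**Conclusion.** The point holds as an inconsistency in the current text. For a subject who failed screening because of a skin lesion and is re-screened within 90 days, Section 8.1.2 and the waiver sentence of Table 1 footnote 7 say that no repeat dermatological examination is needed, while Section 7.3.12 and Appendix 15 say that one is.

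Its size is small. The number of such subjects is not given and cannot be derived from the protocol. Harm requires a site to follow the visit list alone and the error to pass the sponsor's authorization and the criterion 10 checks. The gap arises before randomization to blinded treatment, so it gives no reason to expect bias between the arms; at most it adds pre-existing lesions to the skin malignancy counts. Sample size, power, alpha and the efficacy analyses are untouched. It is a minor correction, worth making because it concerns eligibility and a safety event of special interest.

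**What to change.** Reconcile Section 8.1.2 and Table 1 footnote 7 with Section 7.3.12 and Appendix 15, so that one rule governs the repeat skin examination at re-screening and all four places state it or refer to it. The content of that rule is for the sponsor to settle; the purpose given in the amendment rationale is the natural reference. Stating the rule once and having the visit list and the footnote cite it would keep later amendments from separating them again.

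The cost is wording in one visit list and one footnote. If the reconciled rule is the one Section 7.3.12 already states, it adds no examination beyond those that section already requires. Criterion 9 needs no change on this account.
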